1.2 Schema

Abbreviations: MDS = myelodysplastic syndrome; N = number of patients; RARA = retinoic acid receptor alpha.

CONFIDENTIAL Protocol SY-1425-301, Version 4.1

1.3 Schedule of Activities

	Pre- screening (a) Day -45 to C1D1	Screening (a) Day -30 to C1D1		•				End of Treatment (EoT) (c)	Safety Follow- up (d) 30d post EoT (±3d)	Disease Follow- up (e) q3mo post EoT (±14d)	Survival Follow- up (f) q3mo post EoT (±14d)		
Study Day			D1 (g)	D2-7 (±2d)	D8 (±1d)	D22 (±1d)	D1 (±3d)	D2-7 (±2d)	D15 (±2d) (h)				
Pre-screening Informed Consent	X												
Main Informed Consent		X											
Eligibility Review (i)		X	X (i)										
Eligibility Approval Form (i)		X	X (i)										
Randomization (j)			X										
Medical History (k)		X	X										
Demographics		X											
ECOG Status		X	X				X			X	X		
Height		X											
Weight		X	X		X	X	X			X	X		
Vital Signs (l)		X	X	X (1)	X	X	X	X (1)	X	X	X		
Physical Examination (m) (n)		X	X		X (n)	X (n)	X (n)			X	X	X (n)	
Hematology (o), (p), (q)		X (p)	X		X	X	X (q)			X	X	X	

	Pre- screening (a) Day -45 to C1D1	Screening (a) Day -30 to C1D1			cle 1 Days		Cycles 2+ 28 Days Each (b)			End of Treatment (EoT) (c)	Safety Follow- up (d) 30d post EoT (±3d)	Disease Follow- up (e) q3mo post EoT (±14d)	Survival Follow- up (f) q3mo post EoT (±14d)
Study Day			D1 (g)	D2-7 (±2d)	D8 (±1d)	D22 (±1d)	D1 (±3d)	D2-7 (±2d)	D15 (±2d) (h)				
Serum Chemistries (o)		X	X		X	X	X			X	X		
Coagulation (o)		X	X				X			X	X		
Triglycerides, Total Cholesterol (o)		X	X				X			X	X		
Hepatitis Panel (r)		X											
Urinalysis (o)		X	X				X			X	X		
Pregnancy Test (s)		X	X				X			X	X		
Triplicate ECG (t)		X			X	X			X				
AE Monitoring (u)			X	X	X	X	X	X	X	X	X		
Prior/Concomitant Medication Review (v)		X	X	X	X	X	X	X	X	X	X		
RBC and Platelet Transfusions Recorded (w)		X	X	X	X	X	X	X	X	X	X	X	
Dosing Compliance/Diary Review					X	X	X		X	X			
HRQOL (EORTC QLQ-C30, EQ-5D-5L)		X	X				X			X	X	X	
Subsequent Anticancer Therapies (x)											X	X	X

CONFIDENTIAL

	Prescreening (a) Day -45 to C1D1	Screening (a) Day -30 to C1D1							End of Treatment (EoT) (c)	Safety Follow- up (d) 30d post EoT (±3d)	Disease Follow- up (e) q3mo post EoT (±14d)	Survival Follow- up (f) q3mo post EoT (±14d)	
Study Day			D1 (g)	D2-7 (±2d)	D8 (±1d)	D22 (±1d)	D1 (±3d)	D2-7 (±2d)	D15 (±2d) (h)				
Response Assessment (q), (y)							X (q), (y)			X (y)		X (y)	
Bone Marrow Aspirate		X (z)					X (aa)			X (aa)		X (bb)	
Transformation into AML							X			X		X	X
Overall Survival													X
Tamibarotene or Placebo (cc)					Dosii	ng D8-2	28 of ea	ich Cyc	le (cc)				
Azacitidine (dd)			X	X (dd)			X	X (dd)					
Blood Sample for RARA Biomarker Test (ee)	X									X			
Blood Sample for Exploratory Research (ff)	X		X							X			
Blood Sample for CDx Development	X												
Peripheral Blood for PK (gg)					X	X							

Abbreviations: AE = adverse event; AML = acute myeloid leukemia; CBC = complete blood count; CDx = companion diagnostic; CR = complete remission; CXDX = Cycle X, Day X; D/d = day(s); ECOG = Eastern Cooperative Oncology Group; eCRF = electronic case report form; ECG = electrocardiogram; EDC = electronic data capture [system]; EORTC QLQ-30 = European Organization for Research and Treatment of Cancer Quality of Life Core Questionnaire 30; EoT = End of Treatment; EQ-5D-5L = EuroQol 5 dimensions; HRQOL = health-related quality of life; HSCT = Hematopoietic stem cell transplantation; IWG = International Working Group; MDS = myelodysplastic syndrome; OS = overall survival; PK = pharmacokinetic(s); q3mo = every 3 months; RBC = red blood cell; RARA = retinoic acid receptor alpha; SAE = serious adverse event.

- (a) Pre-screening assessments to ensure patients are RARA-positive will be performed within 45 days of Cycle 1 Day 1 and screening assessments for all other eligibility criteria will be performed within 30 days of C1D1. Screening assessments may occur on C1D1 but must be completed and results reviewed prior to dosing on C1D1. Screening assessments performed within 30 days of C1D1 as part of standard of care are acceptable to support eligibility review.
- (b) Cycle 2 schedule should be followed for all subsequent cycles.
- (c) An EoT Visit should occur within 3 days of the last dose of study drug (or within 3 days of decision to permanently stop study drug treatment, if this decision directly follows a period when study drug has been on hold) and before the start of any subsequent anticancer therapy. If the EoT Visit occurs ≥30 days after the last dose of study drug, it may be combined with the Safety Follow-up Visit.
- (d) A Safety Follow-up Visit should occur after the EoT Visit and if possible, before the start of any subsequent anticancer therapy. If the EoT Visit occurs ≥30 days after the last dose of study drug, it may be combined with the Safety Follow-up Visit.
- (e) Patients who have not progressed/relapsed will enter the Disease Follow-up period. Visits should occur every 3 months for response assessment until disease progression/relapse, death, or the occurrence of the expected number of OS events to support the final OS analysis, whichever occurs first. Disease Follow-up Visit window is ±14 days.
- (f) Patients who progress/relapse will be followed to document the start of subsequent anticancer therapy, the date of disease progression/relapse, the date of transformation to AML, and OS status by telephone (or another appropriate method) until the expected number of OS events to support the final OS analysis is observed. Survival Follow-up Visit contact window is ±14 days.
- (g) C1D1 assessments must be performed prior to study drug administration.
- (h) Cycles 2 through 4 only.
- (i) Eligibility review and approval by Sponsor or designee (via Eligibility Approval Form) must be completed prior to randomization.
- (j) Patients can be randomized earlier than C1D1, but within 72 hours of the first dose of study drug, to accommodate operational needs.
- (k) For all randomized patients, any untoward medical occurrences that happen before the first dose of the study drug should be captured as a part of medical history.
- (l) If administration of the 6th and 7th doses of azacitidine of the cycle is delayed to Days 8 and 9 (see footnote (dd)), the vital sign evaluation will shift from Days 6 and 7 to Days 8 and 9 to parallel azacitidine administration. C1D8 vital sign evaluation is required for all patients.
- (m) Definitions for the "full" and "abbreviated" physical examination are provided in Section 8.2.3; both must include an assessment for the presence of extramedullary AML.
- (n) Abbreviated physical examination will be performed at C1D8, C1D22, D1 of Cycles 2+, and at each Disease Follow-up Visit (see Section 8.2.3).
- (o) Laboratory assessments will be performed locally.
- (p) Screening hematology parameter evaluation must be performed prior to or at least 7 days following any blood product transfusion.
- (q) Additional unscheduled hematology evaluations may be performed up to 2 weeks after the bone marrow aspiration, for those patients in marrow CR without full peripheral blood count recovery at the time of the bone marrow aspirate, to assess whether they meet IWG criteria for CR.
- (r) See Section 10.2 for details.
- (s) A pregnancy test (high-sensitivity urine or serum) must be performed for women of childbearing potential.
- (t) ECGs should be performed after an approximately 10-minute rest period.
- (u) AEs and SAEs will be captured from the time of the first study drug administration through the Safety Follow-up Visit.
- (v) Every medication within 30 days of C1D1 or at any time during the course of the study treatment, up to the **Safety Follow-up Visit**, must be documented.
- (w) All RBC and platelet transfusions received by the patient from 16 weeks prior to randomization through the Disease Follow-up period will be recorded. Per the IWG 2006 response criteria, RBC transfusions entered into the corresponding eCRF in EDC should include only those administered for a hemoglobin level of ≤9 g/dL.
- (x) Subsequent anticancer therapies (including allogeneic HSCT) following EoT will be recorded.

- (y) Response assessments will be performed on D1 of Cycles 2 and 4, followed by every third cycle (7, 10, 13, etc.), at the EoT Visit and at each Disease Follow-up Visit, with additional assessments performed if clinically determined. Following the C7D1 response assessment, those in CR may have the frequency of bone marrow aspirates for response assessment reduced to every 6 cycles, with intervening response assessments based on hematology evaluation and physical examination findings.
- (z) A screening bone marrow aspirate will be performed, with samples for local assessment of **blast count**, **cytogenetics**, **MDS-associated gene mutations**, and **immunophenotype**. A bone marrow biopsy may be performed at investigator's discretion to supplement the interpretation of the bone marrow aspirate. In addition, it is mandatory that an aspirate smear will be sent to the **Central Laboratory** for **central morphologic review**. An additional aspirate sample should be collected if possible and sent to the **Central Laboratory** for **exploratory analyses**. Bone marrow aspirate smears collected within 30 days of Cycle 1 Day 1 as a part of standard of care (pre-consent) are acceptable to support both local assessments and central review.
- (aa) Response assessment bone marrow aspirates will be collected on Day 1 of Cycles 2 and 4, followed by every third cycle (7, 10, 13, etc.), and at EoT, with bone marrow aspirates collected at other times as clinically determined. Following the C7D1 response assessment, those in CR may have the frequency of bone marrow aspirates for response assessment reduced to every 6 cycles. The samples for the local assessment of response (blast count and cytogenetics) are required. In addition, an aspirate smear will be collected and sent to the Central Laboratory for central review. At C4D1, C7D1, every 6 cycles thereafter, as well as at EoT, an additional aspirate sample will be collected and sent to the Central Laboratory for exploratory analyses (Section 8.6.3). A bone marrow biopsy may be performed at investigator's discretion to supplement the interpretation of the bone marrow aspirate.
- (bb) Response assessment bone marrow aspirates will be collected every 3 months during the Disease Follow-up period, with bone marrow aspirates collected at other times as clinically determined. Patients in CR may have the frequency of bone marrow aspirates for response assessment reduced to every 6 months. The samples for the local assessment of response (**blast count** and **cytogenetics**) are required. In addition, an aspirate smear for **central review** will be collected and sent to the Central Laboratory. An additional aspirate sample should be collected if possible and sent to the Central Laboratory for exploratory analyses (Section 8.6.3). A bone marrow biopsy may be performed at investigator's discretion to supplement the interpretation of the bone marrow aspirate.
- (cc) The morning dose of tamibarotene/placebo will be taken in the clinic on C1D8, C1D22, and D15 of Cycles 2 through 4; date/time of dose should be recorded.
- (dd) If dosing on Days 6 and 7 of a cycle is not possible due to logistical limitations, these doses may be delayed to Days 8 and 9. Tamibarotene/placebo is permitted to overlap with azacitidine on Days 8 through 9 of this alternative schedule. If criteria for azacitidine dose hold are met (Table 1), tamibarotene/placebo dosing may continue, unless criteria for tamibarotene/placebo hold are also met. D1 of the next treatment cycle is delayed until azacitidine dosing may resume.
- (ee) Peripheral blood samples will be sent to the Almac Diagnostics Laboratory for assessment of RARA biomarker to determine study eligibility.
- (ff) For evaluation of MDS molecular features associated with response to drug treatment and loss of response to drug treatment (Section 8.6.3).
- (gg) The morning dose of tamibarotene/placebo will be taken in the clinic on C1D8 and C1D22; date/time of dose should be recorded. The date/time of the C1D21 evening dose of tamibarotene/placebo should also be recorded. Three PK blood samples should be obtained on C1D8 and on C1D22, and collection time/date recorded: 1) pre-dose; 2) 1 hour post-dose (±30 min); 3) 3 hours post-dose (±30 min).

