8.1.5 Blood Product Transfusions

All RBC and platelet transfusions received by the patient from 16 weeks prior to randomization through the Disease Follow-up period will be recorded.

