8.2.1 Prior, Concomitant, and Subsequent Medication Review

Every medication (including over-the-counter or prescription medicines, recreational drugs, vitamins, and/or herbal supplements), vaccines, and blood products used by the patient within 30 days of Cycle 1 Day 1 or at any time during the course of the study treatment, up to the Safety Follow-up Visit, must be documented, including:

- reason for use;
- dates of administration, including start and end dates;
- dosage information, including dose and frequency.

The medical monitor should be contacted if there are any questions regarding concomitant or prior therapy.

Subsequent anticancer therapies (including HSCT) following EoT will be recorded.

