9.4.4 Secondary Endpoints

Transfusion Independence

TI, defined as a period of at least 56 days with no RBC or platelet transfusion since the date of randomization to the last dose of study drug +30 days, the initiation of post-treatment therapy, or death, whichever occurs first.

TI rate (based on receiving neither RBC nor platelet transfusion for a period of at least 56 days) with respective 95% exact binomial CIs will be calculated by treatment group. The stratified CMH test will be applied to compare the TI rates between the 2 treatment groups.

Overall Response

Overall response, defined as achievement of CR, PR, marrow CR (mCR), or HI as determined by the investigator per the modified IWG MDS criteria (Cheson 2006).

Overall response rate (ORR) and 95% exact binomial CIs will be calculated by treatment group. The stratified CMH test will be applied to compare the ORRs between the 2 treatment groups. The rates of CR or PR; rates of CR, PR, or marrow CR; and the rates of HI will also be summarized with 95% exact binomial CIs and compared between the treatment groups using the stratified CMH test.

Overall response may also be analyzed in line with the updated IWG response criteria (Zeidan 2023).

Duration of Complete Remission

DOCR, defined as the duration from the date of first documented evidence of CR to the date of documented relapse of disease, as determined by the investigator per the modified IWG MDS criteria (Cheson 2006), or death due to any cause, whichever occurs first.

Kaplan-Meier estimation of median DOCR and corresponding 95% CIs will be presented by treatment group.

Duration of Overall Response

Duration of overall response defined as the duration from the date of first documented evidence of CR, PR, mCR, or HI, to the date of documented disease progression, relapse of disease as determined by the investigator per the modified IWG MDS criteria (Cheson 2006), or death due to any cause, whichever occurs first.

Kaplan-Meier estimation of median duration of overall response and corresponding 95% CIs will be presented by treatment group.

Time to CR

Time to CR, defined as the duration from the date of randomization to the date of the first documented evidence of CR as determined by the investigator per the modified IWG MDS criteria (Cheson 2006).

Time to CR will be summarized descriptively for the 2 treatment groups.

Time to Initial Response

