	Relevant reduction of units of red blood cell (RBC) transfusions by an absolute number of at least 4 RBC transfusions/8 week compared with the pretreatment transfusion number in the previous 8 weeks. Only RBC transfusions given for a Hgb of \leq 9.0 g/dL pretreatment will count in the RBC transfusion response evaluation.
Platelet Response (pretreatment <100 × 10 ⁹ /L)	Absolute increase of $\geq 30 \times 10^9/L$ if starting with $\geq 20 \times 10^9/L$ platelets
	Increase from $<20 \times 10^9/L$ to $>20 \times 10^9/L$ and by at least 100%
Neutrophil Response (pretreatment <1 × 10 ⁹ /L)	At least a 100% increase and an absolute increase $>0.5 \times 10^9/L$
Progression or relapse after HI in the absence of	At least one of the following:
another explanation	At least 50% decrease from maximum response levels in granulocytes or platelets;
	Reduction in Hgb by ≥1.5 g/dL;
	Transfusion dependence.

Adapted from: Cheson BD, Greenberg PL, Bennett JM, Lowenberg B, Wijermans PW, Nimer SD, et al. Clinical application and proposal for modification of the International Working Group (IWG) response criteria in myelodysplasia. *Blood*. 2006;108(2):419-425. Epub 2006 Apr 11.

10.9 Appendix 9: European Organization for Research and Treatment of Cancer Quality of Life Core Questionnaire 30 (Sample)

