7.1.3.9 Post-Baseline Missing Values

- If post-baseline Common Terminology Criteria for Adverse Events (CTCAE) grade for laboratory parameters is missing, there will be no imputation for missing values, and in the shift from baseline to worst post-baseline CTCAE grade by parameter tables, a missing category will be added in order to have the total number of postbaseline participants equal to the total number at baseline.
- Missing category for post-baseline values will be added to ECG shift table, similar to the bullet above. The same rules will be applied for vital sign shift tables and ECOG shift tables.
- If AE grade is missing, the previous worst grade under the same preferred term (PT) will be assigned if it is available, otherwise a grade of 4 will be assigned for classification purpose in the tables, figures, and listings.
- If the transfusion eCRF page is missing or if the blood product received information is missing, then there will be no imputation, and the participants will be classified as having missing transfusion dependence status. If the date of the transfusion is missing, then the transfusion dependence status at baseline and post-baseline will both be missing.

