7.3.8 Prior and Concomitant Blood Transfusions

Any transfusions from 16 weeks prior to randomization through the Disease Follow-up period will be recorded. Transfusions will be classified as prior or concomitant based on the start date. A prior transfusion is defined as any transfusion that started up to 16 weeks prior to the date of randomization. A concomitant transfusion is defined as any transfusion that started on or after the date of randomization through the Disease Follow-up period. Prior and concomitant blood transfusions will be summarized separately.

For both prior and concomitant transfusion summaries, the number and percentage of participants receiving any RBC or platelet transfusion will be summarized by treatment group and overall, as will the number and percentage by transfusion type (RBCs, platelets, or other blood product). Participants with more than 1 transfusion at each level of summarization (any transfusion received, transfusion type) will be counted only once. Additionally, transfusion burden (units/56 days) will be summarized using descriptive statistics as part of the prior transfusion and concomitant blood transfusion units received from 16 weeks prior to randomization to randomization for prior transfusion, and the total number of transfusion units received from randomization through Disease Follow-up period for concomitant blood transfusion. Transfusion burden will be analyzed by each 56 days blocks for both prior transfusion and concomitant blood transfusion. The study phase during which each transfusion was received (e.g., prior or concomitant) will be presented on the listing of blood transfusions.

mITT and ITT analysis sets will be used for prior and concomitant blood transfusions analysis.

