7.4.6.7 Transfusion Rate

Participants who have been on treatment for at least 56 days are considered evaluable for this analysis.

Definitions:

• Baseline Transfusion Dependence:

Transfusion of ≥ 1 unit of RBCs and/or platelets during the 56 days prior to date of randomization.

• Baseline TI:

No RBC or platelet transfusions during the 56 days prior to date of randomization.

• Post-baseline TI:

Post-baseline TI is defined as a period of at least 56 days with no RBC or platelet transfusion since the date of randomization to the last dose of study drug + 30 days, the initiation of post-treatment therapy, or death, whichever occurs first.

Analyses:

The mITT Analysis Set will be used for the following transfusion rate analyses.

Overall transfusion status (RBC or platelets), RBC transfusion status, and platelet transfusion status will be analyzed separately as below:

• Rate of conversion of baseline transfusion dependence to post-baseline TI in the baseline transfusion-dependent mITT participants.

The number and percentage of mITT participants who are transfusion dependent at baseline and the number and percentage of baseline transfusion-dependent mITT participants who achieved post-baseline TI, along with respective 95% exact binomial CIs, will be summarized by treatment group.

• Rate of maintenance of baseline TI in the baseline transfusion-independent mITT patients.

The number and percentage of mITT participants who are transfusion independent at baseline and the number and percentage of baseline transfusion-independent mITT participants who maintained TI post-baseline will be summarized by treatment group.

In addition, the median number of units of RBC and platelets received in 56 days blocks (e.g., Day 1 to Day 56, Day 57 to Day 112, and etc.) starting from Cycle 1 Day 1 will be reported for each treatment group.

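### Footnote (w) keeps RBC transfusions given above 9 g/dL out of the eCRF, although transfusion independence, baseline dependence and transfusion burden count every transfusion

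*Protocol*

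**What the plan says.** Footnote (w) in Protocol Section 1.3 holds two instructions. The first is the rule repeated in Section 8.1.5: "All RBC and platelet transfusions received by the patient from 16 weeks prior to randomization through the Disease Follow-up period will be recorded". The second, attributed to the IWG 2006 criteria, is that "RBC transfusions entered into the corresponding eCRF in EDC should include only those administered for a hemoglobin level of ≤9 g/dL". Platelet transfusions are not restricted. SAP Section 7.3.8 again assumes that any transfusion is recorded, and Protocol Section 10.1.6 places all patient data in eCRFs.

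The hemoglobin limit has one source in the documents. In Protocol Appendix 8 (repeated in SAP Table 8), the transfusion-reduction criterion for erythroid response says that RBC units given at 9.0 g/dL or lower "pretreatment will count in the RBC transfusion response evaluation".

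The transfusion analyses carry no such limit:

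- **Transfusion independence**, Protocol Section 9.4.4: "TI, defined as a period of at least 56 days with no RBC or platelet transfusion since the date of randomization", with the window closing at the earliest of 30 days after last dose, start of post-treatment therapy, and death. SAP Section 7.4.5.1 uses the same definition.
- **Baseline TI**, SAP Section 7.4.6.7: "No RBC or platelet transfusions during the 56 days prior to date of randomization". Baseline dependence is one or more units in the same window.
- **Burden**, SAP Section 7.3.8: "Transfusion burden will be analyzed by each 56 days blocks for both prior transfusion and concomitant blood transfusion".

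On missing data, SAP Section 7.1.3.9 says: "If the transfusion eCRF page is missing or if the blood product received information is missing, then there will be no imputation", and status is then set to missing. A missing transfusion date is treated likewise.

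**The concern.** A site cannot obey both sentences of footnote (w). The second turns a filter meant for one derivation into an entry rule for the data behind every transfusion analysis. Protocol Section 6.8.6 leaves RBC transfusion to clinical judgment, so transfusions above 9 g/dL can occur.

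The missing-data rule would not catch the loss. It acts when the page, the product information or the date is absent. A transfusion left out under footnote (w) triggers none of these.

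TI is a secondary endpoint compared between arms by a stratified CMH test at the two-sided 5% level (SAP Sections 7.1.1 and 7.4.5.1), outside the CR and OS testing hierarchy. Baseline dependence defines the denominators for the conversion and maintenance rates. SAP Section 6.4.1.1 also requires counts supporting CR to be free of transfusion for the previous 7 days, which a restricted page alone cannot fully confirm.

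**Working it through.** The documents give no TI rate, transfusion rate or TI power, so there is no planned figure to reproduce. The check covers direction first, then size under stated assumptions.

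**Direction.** A patient is TI if the longest transfusion-free run in the window is at least 56 days. The end of the window does not depend on transfusion records, so deleting a record can only lengthen a run. For example, take RBC transfusions on days 20, 50 and 80 of a 100-day window. The longest run is 80 − 50 − 1 = 29 days: not TI. If the day-50 unit was given above 9 g/dL and is not entered, the run is 80 − 20 − 1 = 59 days: TI. In 200,000 random histories with records deleted at random, none moved from TI to non-TI and 12,278 moved from non-TI to TI.

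**Size.** Assumptions: RBC transfusions are Poisson at r per 56 days, uniform in time, with the same rate for every patient and no platelet transfusions. Each is omitted with probability s, the share given above 9 g/dL, assumed to be 2% to 15%. There were 40,000 simulated patients per cell. Entries are recorded minus true TI, in percentage points:

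| Window | r | s = 2% | 5% | 10% | 15% |
|---|---|---|---|---|---|
| 168 days | 1 | 0.46 | 1.04 | 2.15 | 3.21 |
| 168 days | 2 | 1.23 | 3.13 | 6.36 | 9.55 |
| 168 days | 3 | 1.37 | 3.43 | 6.99 | 10.84 |
| 168 days | 4 | 1.02 | 2.64 | 5.59 | 8.97 |
| 336 days | 1 | 0.04 | 0.09 | 0.19 | 0.29 |
| 336 days | 2 | 0.90 | 2.06 | 3.78 | 5.57 |
| 336 days | 3 | 1.87 | 4.50 | 9.09 | 13.44 |
| 336 days | 4 | 1.75 | 4.66 | 9.72 | 15.13 |

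At r = 1 true TI is already 90.1% (168 days) and 99.5% (336 days), which leaves little room for excess.

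**Baseline window.** The extra probability that the 56 days before randomization appear transfusion-free is exp(−r(1 − s)) − exp(−r).

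- r = 1, s = 0.02: exp(−0.98) − exp(−1) = 0.74 points. At s = 0.15: exp(−0.85) − exp(−1) = 5.95 points.
- r = 4, s = 0.02: exp(−3.92) − exp(−4) = 0.15 points. At s = 0.15: exp(−3.4) − exp(−4) = 1.51 points.

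**Burden.** Recorded RBC units fall by about s, so 2% to 15%, if units per transfusion do not depend on hemoglobin.

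**Arm difference.** With the same omission share in both arms, the true difference becomes the recorded difference as follows (separate runs for each share):

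| Rates per 56 days, window | s = 5% | s = 15% |
|---|---|---|
| 3 vs 4, 168 days | 16.6 to 17.5 | 16.8 to 19.2 |
| 2 vs 3, 336 days | 27.4 to 25.3 | 27.5 to 19.5 |
| 1 vs 2, 168 days | 29.6 to 27.7 | 29.7 to 23.5 |

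In a separate model with platelets and varying patient rates, a true difference of about 4 points was recorded as 3 to 4 points at equal omission of 10% to 30%. It was recorded as 6.9 points at 30% versus 10% (tamibarotene versus placebo) and 0.3 points at 10% versus 30%.

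**The case against.** The strongest reply is that a second record exists. Protocol Section 8.2.1 requires documentation of "vaccines, and blood products used by the patient within 30 days of Cycle 1 Day 1" and onward to the Safety Follow-up Visit, with dates and dose. That visit falls about 30 days after an End of Treatment Visit held within 3 days of last dose, so the record covers essentially the whole TI window. This stands: omitted on-study transfusions should be largely recoverable. But the SAP does not link these records to TI, and nothing tells anyone to reconcile them. They also begin only 30 days before Cycle 1 Day 1, short of the 56-day baseline window and the 16-week look-back.

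A related point is that SAP Section 7.4.5.1 names no source page for TI; reliance on the transfusion page is inferred from Section 7.1.3.9. That is fair, although it is the page on which the SAP's own missing-status rule rests.

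The larger figures depend on the model. At 15% omission, four RBC transfusions per 56 days and 336 days, a rerun gave an excess of 14.9 points. Adding two platelet transfusions per 56 days cut this to 4.7. Letting patient rates vary (gamma, shape 1), without platelets, cut it to 5.5. With varying rates, the excess never exceeded 5.5 points at 15% omission or 2.0 at 5%. Platelets do not always reduce it: at one RBC plus one platelet transfusion per 56 days over 168 days, the excess rose from 3.1 to 5.1. The upper end of the table is therefore an extreme case.

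Finally, the effect requires sites to follow the second sentence over the first, and some transfusions to be given above 9 g/dL. Neither is known. If sites differ in which sentence they follow, the data are inconsistent between sites instead.

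**Conclusion.** The concern holds. The entry rule contradicts the sentence before it, Protocol Section 8.1.5 and SAP Section 7.3.8, and it applies the IWG limit beyond the criterion to which it belongs. Where it is followed, recorded overall TI and RBC TI are at or above their true values in each arm. Platelet TI is unaffected. Some baseline-dependent patients are classed as independent, and RBC burden is understated.

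The direction within each arm is certain, provided an omitted transfusion is read as none. The size is not known. A few points is plausible under the assumed 2% to 15% share, with about 15 points only in a homogeneous, platelet-free model. No direction is claimed for the arm difference or for the conversion and maintenance rates. An effect on CR is possible but not shown, since CR is investigator-determined and Section 8.2.1 records exist. Because TI is outside the alpha hierarchy, this should be fixed but does not threaten the primary test.

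**What to change.** 1. Delete the entry restriction in footnote (w) and align the eCRF completion guidelines. Every RBC and platelet transfusion is entered with date, units and, for RBC, pre-transfusion hemoglobin.
2. Apply the 9 g/dL limit only in the program that derives the erythroid transfusion-reduction criterion.
3. State in the SAP that TI, baseline dependence, transfusion burden and the 7-day check for CR use all transfusions.
4. Before database lock, back-enter omitted transfusions from source documents or the Section 8.2.1 records. Source documents are needed for the part of the look-back that Section 8.2.1 does not reach.

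The cost is a footnote and guideline edit, one derivation filter, one SAP sentence and some retrospective data entry. There is no extra patient procedure and no change to transfusion practice.
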